## 1. Protocol Synopsis

### Title of Study:

A Single Dose Pharmacokinetic Study of Tirzepatide in Subjects with Varying Degrees of Hepatic Impairment

### Rationale:

Tirzepatide (LY3298176) is a dual agonist of glucose-dependent insulinotropic polypeptide and glucagon-like peptide-1 receptors being developed for the treatment of type 2 diabetes mellitus. As the patient population for tirzepatide may include patients with hepatic impairment, it is important to ascertain whether tirzepatide can be safely prescribed to this population without dose adjustment, once marketed. The fatty acid component of tirzepatide is expected to bind to albumin; however, albumin concentration in hepatic impaired subjects can be lower than that seen in control subjects. Therefore, this study will evaluate the pharmacokinetics (PK) of tirzepatide in subjects with hepatic impairment compared to healthy control subjects to investigate the impact of hepatic impairment, if any, on the PK of tirzepatide.

### Objectives/Endpoints:

Objectives	Endpoints
Primary To evaluate the PK of a single SC dose of tirzepatide in subjects with mild, moderate, and severe hepatic impairment compared to control subjects with normal hepatic function.	AUC( $0-\infty$ ) and $C_{max}$
Secondary To evaluate the safety and tolerability of a single SC dose of tirzepatide in subjects with mild, moderate, and severe hepatic impairment compared to control subjects with normal hepatic function.	Incidence of AEs

Abbreviations: AE = adverse event; AUC( $0-\infty$ ) = area under the drug concentration-time curve from zero to infinity;  $C_{max}$  = maximum observed drug concentration; PK = pharmacokinetics; SC = subcutaneous.

### Summary of Study Design:

Study I8F-MC-GPGQ will be a multicenter, parallel, single-dose, open-label, single-period study of tirzepatide in subjects with normal hepatic function and subjects with mild, moderate, and severe hepatic impairment. Subjects enrolled in Group 1 (normal hepatic function) will be matched by weight ( $\pm 10$  kg), age ( $\pm 10$  years), and sex to subjects with hepatic impairment, as far as practically possible.

Subjects will undergo a screening examination within 28 days prior to enrollment, check in to the clinical research unit (CRU) on Day -1, and receive a single subcutaneous dose of 5 mg tirzepatide on Day 1, following an overnight fast of at least 8 hours. Subjects will remain at the CRU until discharge on Day 5, and return to the CRU on Days 8 and 15 for PK blood sampling and other study procedures. Each subject will be required to return to the CRU for a follow-up visit and final PK blood sample collection at least 28 days postdose.

### Treatment Arms and Planned Duration for an Individual Subject:

Subjects will be enrolled within the following groups:

Group 1: at least 6 subjects and up to 12 subjects with normal hepatic function (Control).

Group 2: at least 6 subjects with mild hepatic impairment (Child Pugh [CP] A).

Group 3: at least 6 subjects with moderate hepatic impairment (CP B).

Group 4: up to 6 subjects with severe hepatic impairment (CP C).

Efforts will be made to achieve 6 completers with severe hepatic impairment (Group 4); however, acknowledging the difficulty in recruiting this subject population, 2 to 3 subjects with severe hepatic impairment may be an acceptable target.

Subjects with normal hepatic function cannot be matched to more than 1 hepatically-impaired subject within an impairment group; however, subjects with normal hepatic function may be matched to 1 subject from more than 1 hepatic impairment group, therefore requiring fewer subjects to be enrolled to Group 1 (minimum of 6). Subjects may be replaced at the discretion of the investigator in discussion with the sponsor.

The total duration of study participation for each subject (from screening through follow-up visit) is anticipated to be approximately 8 weeks.

**Number of Subjects:**

Up to 30 subjects may be enrolled to achieve the target minimum number of completers in each of the 4 study groups.

**Statistical Analysis:**

**Pharmacokinetic:** Blood samples will be collected for the measurement of tirzepatide concentrations, using validated liquid chromatography tandem mass spectrometry methods. Pharmacokinetic parameter estimates for tirzepatide will be calculated by standard noncompartmental methods of analysis. The primary parameters analyzed will be maximum observed drug concentration ( $C_{max}$ ) and area under the drug concentration-time curve from zero to infinity ( $AUC[0-\infty]$ ). Other noncompartmental parameters may be reported as appropriate.

The primary PK analysis is the evaluation of log-transformed  $AUC(0-\infty)$  and  $C_{max}$  using an analysis of covariance (ANCOVA) model with hepatic function group as a fixed factor and body weight as a covariate. The geometric least squares means for each group, geometric least squares mean ratios between each hepatic impairment level versus the control group, and the corresponding 90% confidence intervals will be estimated from the ANCOVA model. In the event of dose adjustment based on the interim analyses results, dose normalized PK parameters may be used in the above model. The analysis of  $t_{max}$  will be based on a nonparametric method. Medians and differences in medians for hepatic function groups and the p-value from a Wilcoxon rank sum test will be presented.

The relationship between the PK parameters and Child-Pugh Classification parameters (serum albumin concentration, total bilirubin concentration, and prothrombin time) will be assessed graphically. The PK parameters  $AUC(0-\infty)$ ,  $C_{max}$ , and apparent clearance will be plotted against each Child-Pugh Classification parameter separately.

Additional PK parameters may be analyzed if deemed appropriate following a review of the data.

**Safety:** All investigational product and protocol procedure adverse events will be listed and, if the frequency of events allows, safety data will be summarized using descriptive methodology.

## 2. Schedule of Activities

## Study Schedule Protocol I8F-MC-GPGQ

Procedure	Screening	Study Days							Follow-up or ED c	Comments
	D-29 to D-2	D-1	D1	D2	D3	D4	D5	D8	D15	
Informed Consent	X									
Subject Admission to CRU		X								
Tirzepatide Administration			X (0 hour)							Study drug will be administered after an overnight fast of at least 8 hours.
Subject Discharge from CRU						X				Subjects may be required to stay longer in the CRU at the investigator's discretion for safety monitoring.
Outpatient Visit	X						X	X	X	
Medical History	X									
Physical Examination	X	X					X	X	X	After screening, medical assessment only performed to include medical review and targeted examination, as appropriate.
Weight	X	X							X	
Height	X									
Temperature	X	X								
Urine Drug Screen	X	X					X	X		
Ethanol Testing		X					X	X		
Safety 12-lead ECG (hours)	X		Predose		48		X		X	Single ECG will be collected. ECGs must be recorded before collecting any blood samples. Subjects must be supine for approximately 5 to 10 minutes before ECG collection, and remain supine but awake during ECG collection.
Supine Vital Signs (hours) a	X	X	Predose, 12	24	48	72	96	X	X	Additional time points may be added, if warranted and agreed upon between Lilly and the investigator.
Clinical Laboratory Tests b	X	X			X		X	X	X	See Appendix 2 for details. Day -1 samples may be collected between Day -4 to Day -1, provided that the results are reviewed prior to actual dosing on Day 1.
Child-Pugh Classification	X	X								
Pregnancy Test	X	X					X	X		Female subjects only. See Appendix 2 for details.
AEs/Concomitant Medications	X	X	X	X	X	X	X	X	X	
Pharmacogenetic Sample			Predose							Single sample for pharmacogenetic analysis.

Procedure	Screening	Study Days									Follow-up or ED c	Comments
	D-29 to D-2	D-1	D1	D2	D3	D4	D5	D8	D15			
Immunogenicity (hours)			Predose							X	X	Where applicable, collection times should match with PK sampling time points. In the event of drug hypersensitivity reactions (immediate or non-immediate), samples will be collected as close to event onset as possible, at event resolution, and 30 ( $\pm$ 3) days following the event. Subjects with TE ADA at follow-up/ED will undergo additional follow-up. See Section 9.6.1 for details.
Blood Glucose Monitoring (hours)			Predose, 8, 12	24, 36	48	72	96	X	X	X		Performed using a bedside glucose monitor. Additional measurements may be taken at the discretion of the investigator as clinically indicated.
PK Sampling (hours)			Predose, 8, 12	24	48	72	96	168	336	X		The exact time of sampling must be recorded.

Abbreviations: AE = adverse event; CRU = clinical research unit; D = day; ECG = electrocardiogram; ED = early discontinuation; PK = pharmacokinetic(s);

TE ADA = treatment-emergent antidrug antibodies.

Note: All sampling times are given relative to dosing (Time 0 hour) with tirzepatide (predose or hours postdose).

If multiple procedures take place at the same time point, the following order of the procedures should be used: ECGs, vital signs, clinical laboratory sample, PK sample (record of actual PK sampling time is the priority), immunogenicity, blood glucose and pharmacogenetic sample.

a Specified times are approximate and actual times will be recorded. Actual time should not exceed 1 hour prior to dosing for the predose assessment.

b Screening sample and any unscheduled samples for immediate safety assessments may be performed by the local laboratory affiliated with the sites. All other scheduled clinical safety laboratory samples will be assayed by a central laboratory for study reporting purpose.

c At least 28 days postdose or within 7 to 14 days upon confirmation of early discontinuation.

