Study GPGA was a combination single-ascending dose (SAD) and a multiple ascending-dose (MAD) study in healthy subjects (Part A and B) and a multi-dose study in patients with T2DM (Part C). The study investigated the safety, tolerability, PK, and pharmacodynamics (PD) of tirzepatide administered as SC injections. Weekly doses of tirzepatide ranged from 0.25 mg to 8 mg in the SAD. Maximum tolerated dose in healthy subjects following single-dose administration was 5 mg. In the 4-week MAD part of the study, doses up to 10 mg in healthy subjects or 15 mg in patients with T2DM were attained via a dose escalation approach. A dose of 15 mg tirzepatide attained by fast dose escalation over 4 weeks (5/5/10/15 mg), while considered to be safe, was associated with high incidence of gastrointestinal (GI) events. Terminal half-life was estimated to be approximately 5 days, thus supporting a once weekly dosing regimen, with maximum observed drug concentration ( $C_{max}$ ) occurring between 24 to 72 hours postdose, and steady-state tirzepatide exposures expected to be attained within 4 weeks of once weekly dosing. Study GPGC was a MAD study to investigate the safety, tolerability, PK, and PD in Japanese patients with T2DM. Overall, tirzepatide PK parameters in Japanese patients with T2DM appeared comparable to corresponding parameters from non-Japanese patients with T2DM observed in Study GPGA.

Gastrointestinal adverse events (AEs) (nausea, vomiting, diarrhea, abdominal distension) and decreased appetite were the most frequently reported events by both healthy subjects and patients with T2DM and were dose related in the two Phase 1 studies. A dose-dependent increase in heart rate was detected for both healthy subjects and patients with T2DM who received tirzepatide, similar to what was observed with selective GLP-1 receptor agonists. A few subjects experienced transient elevations in lipase and/or amylase levels, but these episodes were not associated with any relevant clinical outcomes. There were no other clinically relevant safety observations in the Phase 1 studies.

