## 5. Study Design

### 5.1. Overall Design

This will be a multicenter, parallel, single-dose, open-label, single-period study of tirzepatide in subjects with normal hepatic function and subjects with mild, moderate, and severe hepatic impairment. Subjects who have a concomitant T2DM diagnosis will not be specifically excluded.

Subjects will be enrolled within the following groups:

- Group 1: at least 6 subjects and up to 12 subjects with normal hepatic function (Control).
- Group 2: at least 6 subjects with mild hepatic impairment (Child Pugh [CP] A).
- Group 3: at least 6 subjects with moderate hepatic impairment (CP B).
- Group 4: up to 6 subjects with severe hepatic impairment (CP C).

Efforts will be made to achieve 6 completers with severe hepatic impairment (Group 4); however, acknowledging the difficulty in recruiting this subject population, 2 to 3 subjects with severe hepatic impairment may be an acceptable target.

The Child-Pugh classification is described in Section [5.1.1](#).

[figure not shown]
Subjects enrolled in Group 1 (normal hepatic function) will be matched by weight ( $\pm 10$  kg), age ( $\pm 10$  years), and sex to subjects in Groups 2 through 4, as far as practically possible. Subjects with normal hepatic function cannot be matched to more than 1 hepatically-impaired subject within an impairment group; however, subjects with normal hepatic function may be matched to 1 subject from more than 1 hepatic impairment group, therefore requiring fewer subjects to be enrolled to Group 1 (minimum of 6). Subjects who withdraw before completing all study procedures may be replaced at the discretion of the investigator in discussion with the sponsor.

Subjects will undergo a screening examination within 28 days prior to enrollment, check in to the CRU on Day -1, and receive a single SC dose of 5 mg tirzepatide on Day 1, following an overnight fast of at least 8 hours. Subjects will remain at the CRU until discharge on Day 5, and return to the CRU on Days 8 and 15 for PK blood sampling and other study procedures. Each subject will be required to return to the CRU for a follow-up visit and final PK blood sample collection at least 28 days postdose.

Pharmacokinetic blood sampling and safety assessments, including vital sign measurement, physical examination, clinical laboratory tests, electrocardiograms (ECGs), and AE recording, will be performed according to the Schedule of Activities (Section [2](#)).

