## 8. Discontinuation Criteria

### 8.1. Discontinuation from the Study

Subjects who discontinue the study early will have procedures performed as shown in the Schedule of Activities (Section 2).

Subjects will be discontinued in the following circumstances:

- Enrollment in any other clinical study involving an investigational product or enrollment in any other type of medical research judged not to be scientifically or medically compatible with this study
- Participation in the study needs to be stopped for medical, safety, regulatory, or other reasons consistent with applicable laws, regulations, and good clinical practice (GCP)
- Investigator Decision
  - the investigator decides that the subject should be discontinued from the study
  - if the subject, for any reason, requires treatment with another therapeutic agent that has been demonstrated to be effective for treatment of the study indication, discontinuation from the study occurs prior to introduction of the new agent
- Subject Decision
  - the subject, or legal representative, requests to be withdrawn from the study.

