### **9.2.1. Serious Adverse Events**

An SAE is any AE from this study that results in one of the following:

- death
- initial or prolonged inpatient hospitalization
- a life-threatening experience (that is, immediate risk of dying)
- persistent or significant disability/incapacity
- congenital anomaly/birth defect
- important medical events that may not be immediately life-threatening or result in death or hospitalization but may jeopardize the subject or may require intervention to prevent one of the other outcomes listed in the definition above.

Study site personnel must alert the Lilly CRP/CP, or its designee, of any SAE as soon as practically possible.

Additionally, study site personnel must alert Lilly Global Patient Safety, or its designee, of any SAE within 24 hours of investigator awareness of the event via a sponsor-approved method. If alerts are issued via telephone, they are to be immediately followed with official notification on study-specific SAE forms. This 24-hour notification requirement refers to the initial SAE information and all follow-up SAE information.

Although all AEs are recorded in the eCRF after signing informed consent, SAE reporting to the sponsor begins after the subject has signed informed consent and has received investigational product. However, if an SAE occurs after signing informed consent, but prior to receiving investigational product, AND is considered reasonably possibly related to a study procedure then it **MUST** be reported.

Investigators are not obligated to actively seek AEs or SAEs in subjects once they have discontinued from and/or completed the study (the subject summary eCRF has been completed). However, if the investigator learns of any SAE, including a death, at any time after a subject has

been discharged from the study, and he/she considers the event reasonably possibly related to the study treatment or study participation, the investigator must promptly notify Lilly.

Pregnancy (maternal or paternal exposure to investigational product) does not meet the definition of an AE. However, to fulfill regulatory requirements any pregnancy should be reported following the SAE process to collect data on the outcome for both mother and fetus.

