## Pancreatic Enzymes: Safety Monitoring Algorithm for Subjects/Patients without Symptoms of Pancreatitis

Follow this algorithm when the value(s) for serum lipase and/or amylase are  $\geq 3$  X ULN.

1. Symptomatic – related primarily to abdominal pain consistent with pancreatitis; however, severe nausea, vomiting and other symptoms may be considered by the investigator as symptomatic as well.

2. If, at any time, in the opinion of the investigator, patient/subject has symptoms of acute pancreatitis irrespective of L/A results:

- (a) Consult appropriate specialist for assessment and management
- (b) Assess for causes of pancreatitis
- (c) Stop study drug (if applicable)
- (d) Notify Lilly

3. L/A = Lipase and/or amylase. Either or both enzymes can be measured and either or both can be used to meet the algorithm criteria.

4. Abdominal imaging is most valuable when performed at the time of elevated enzyme values. If in the opinion of the radiologist or investigator, it is safe for the patient/subject to receive contrast, an enhanced abdominal CT is preferred. MRI is also an acceptable imaging modality.

5. As minimum, test hepatic analytes, triglycerides, and calcium, and record all concomitant medications

6. Imaging results positive or negative for signs of acute pancreatitis

Abbreviations: CBC = complete blood count; CT = computed tomography; LFTs = liver function tests; MRI = magnetic resonance imaging.

Subjects diagnosed with pancreatitis will be discontinued from the study. Investigators will be responsible for following, through an appropriate healthcare option, these pancreatitis AEs until the events resolve or are explained. Adverse events that meet the diagnostic criteria of acute pancreatitis will be captured as SAEs. For all other pancreatic AEs (such as idiopathic or asymptomatic pancreatic enzyme abnormalities), the investigator will be responsible for determining the seriousness of the event (AE or SAE) and the relatedness of the event to study drug.

---

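### A dosed subject who leaves within the first days can have the last AE, PK and ADA assessment well short of 28 days postdose, because footnote c of the schedule does not match Section 5.1 (minor)

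*Protocol*

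**What the plan says.** Treatment is one subcutaneous injection on Day 1. Protocol Section 5.1 states the closing visit for everyone, with no exception for early leavers: "Each subject will be required to return to the CRU for a follow-up visit and final PK blood sample collection", at 28 days postdose or later. The synopsis and SAP Section 5 repeat this.

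The Schedule of Activities has a single column for follow-up or early discontinuation (ED). Footnote c times it "At least 28 days postdose or within 7 to 14 days upon confirmation of early discontinuation". Section 8.1 points early leavers there: "Subjects who discontinue the study early will have procedures performed as shown in the Schedule of Activities". Section 9.6.1 likewise takes the closing ADA sample at one visit or the other.

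On adverse events, Section 9.2.1 says: "Investigators are not obligated to actively seek AEs or SAEs in subjects once they have discontinued from and/or completed the study". A parenthesis ties this to completion of the subject summary form. Some departures are mandatory; Appendix 7 says "Subjects diagnosed with pancreatitis will be discontinued from the study".

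On kinetics, Section 3.2 reports "Terminal half-life was estimated to be approximately 5 days", with the peak "occurring between 24 to 72 hours postdose".

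**The concern.** The ED visit is counted from discontinuation, not from the dose. With a single long-acting injection, leaving the study does not end exposure, so a subject who leaves early can have the closing assessment while a material share of the dose is still present. After that visit nobody is required to look for new events.

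The secondary endpoint is the incidence of AEs compared across hepatic function groups, and ADA formation is exploratory. SAP Section 9.5.1 counts treatment-emergent events as those after dosing, with no end to the window and no allowance for length of follow-up. SAP Section 8 puts all enrolled subjects in the safety population. A subject last seen on day 8 postdose and one last seen on day 28 therefore carry the same weight. Departure may also be selective, since medical and safety reasons are among the grounds for it.

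**Working it through.** The documents give no figure for residual drug or for the number of early leavers, so there is nothing to reproduce.

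**Step 1: which visit applies.** Footnote c, the shared column, Section 8.1 and Section 9.6.1 all read as the ED visit standing in place of the 28-day visit. Apart from the general sentence in Section 5.1, nothing requires contact with an early leaver at 28 days postdose.

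**Step 2: drug remaining at the last visit.** Inputs: half-life 5 days (Protocol 3.2) and a visit 7 or 14 days after discontinuation (footnote c). Fraction remaining at t days postdose = 0.5^(t/5). Day 5 is 4 days postdose, Day 8 is 7 and Day 15 is 14.

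| Discontinuation confirmed | 7-day visit | 14-day visit |
|---|---|---|
| Dosing day | t = 7: 0.5^1.4 = 37.9% | t = 14: 0.5^2.8 = 14.4% |
| Day 5 | t = 11: 0.5^2.2 = 21.8% | t = 18: 0.5^3.6 = 8.2% |
| Day 8 | t = 14: 14.4% | t = 21: 0.5^4.2 = 5.4% |
| Day 15 | t = 21: 5.4% | t = 28: 2.1% |

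At 28 days postdose: 0.5^5.6 = 2.1%. A subject leaving 20 days postdose is seen at day 27 to 34, so the visit can fall after day 28.

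**Step 3: sensitivity.** With first-order absorption, the fraction remaining is (ka·e^(−ke·t) − ke·e^(−ka·t))/(ka − ke), where ke = ln 2/5 per day and ka is solved for a peak at 3 days. The first two rows become 47.7% / 18.2% and 27.6% / 10.5%, and the 28-day value 2.6%. With simple decay and a half-life of 4 to 7 days (an assumed range), leaving at Day 5 gives 14.9% to 33.6% at a 7-day visit and 4.4% to 16.8% at a 14-day visit, against 0.8% to 6.2% at 28 days.

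**Step 4: PK.** Under linear kinetics the same fraction is the share of AUC(0-∞) still to come. It exceeds 20% when the last sample is before day 5 × ln(5)/ln(2) = 11.6, or before day 13.3 with a 3-day peak. SAP Section 9.3.1 flags values above 20% extrapolated but does not automatically exclude them.

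**Step 5: what can be missed.**
- *New AEs.* These need not be sought after the last visit. A subject removed because of a postdose AE is already counted in the overall percentage with any AE, so later events cannot change that figure. Event counts and the percentages for other preferred terms can be too low.
- *TE ADA.* Appendix 5 plans three samples. As the schedule table reads, the middle one is on Day 15. A subject leaving before then may have only the ED sample after dosing.

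**Step 6: weight of one subject.** In a group of 6, one leaver is 1/6 = 17%, or 1/7 = 14% if replaced. In a severe group of 2 to 3, the share is 1/2 to 1/3 (50% to 33%), or 1/3 to 1/4 (33% to 25%) if replaced.

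**The case against.** Section 5.1 can be read as the planned course, with footnote c as a specific exception for early leavers that Sections 8.1 and 9.6.1 support. That is a fair reading, but no section states it, and it leaves open whether AEs are sought to 28 days in someone already dosed.

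The safety provisions are also more complete than Section 9.2.1 alone suggests. Section 9.2 follows known events that are serious, medically important or related. Appendix 7 makes the investigator follow pancreatitis until it resolves or is explained. Related SAEs learned of later are reported. Hypersensitivity events are sampled 30 (±3) days afterwards, and clinically significant TE ADA is retested every 3 months. A reader might infer that subjects removed for harm are left without follow-up; these provisions rule that out. They are triggered by findings already made, however, and do not detect new ones.

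Disclosure is partly planned: Section 10.2.1 reports how far each discontinued subject participated, safety is descriptive only, and ADA is exploratory. That lowers the stakes. It does not tell a reader of an AE percentage that some subjects had a shorter window.

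**Conclusion.** The point holds as a minor inconsistency with a cheap remedy. For a dosed subject leaving by about Day 5, the last planned assessment can come with about 22% to 38% of drug remaining (7-day visit) or 8% to 14% (14-day visit), against about 2% at 28 days. Event counts, specific AE terms and TE ADA percentages may then be understated, and AUC(0-∞) may rest on heavy extrapolation.

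Two stronger readings are not supported. A reader might infer that every early leaver is last seen with much of the dose present; a Day 15 leaver is seen with about 5% or less, and later leavers can be seen after day 28. A reader might also infer that the AE percentages are biased downward throughout; the overall percentage with any AE is unaffected for a subject removed because of a postdose AE, and no rate of new late events is given from which to size the rest.

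The figures assume simple exponential decay and a 5-day half-life taken from healthy subjects and patients with T2DM, carried over to hepatic impairment. How many subjects are affected is unknown, out of at most about 30 planned.

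**What to change.** Reconcile footnote c and Section 9.2.1 with Section 5.1. For dosed subjects who have not withdrawn consent, keep the already planned data-collection visit at 28 days or more postdose (AE query, PK and ADA sample) alongside any ED visit, and state in Section 9.2.1 that AEs are sought until then. This concerns data collection only; clinical care after discontinuation is not at issue here.

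In the SAP, footnote the AE tables (9.5.1) and ADA tables (9.4.1) with any subject last seen before 28 days postdose. SAP Section 9.1 ends listings at the point of withdrawal, so it should say that data from a retained visit are included.

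The cost is a few lines of wording, a table footnote, and at most one already planned visit for a few subjects. It cannot reach those who withdraw consent or are lost to follow-up, so the footnote is needed in any case.
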